Comparison of Preoperative Ultrasound Guided Nerve Blocks to Intraoperative Nerve Block Catheters for Breast Reconstruction: A Prospective Randomized Trial

NCT03201809

6/21/2018

PROTOCOL TITLE:

1) Protocol Title

Title: Comparison of Preoperative Ultrasound Guided Nerve Blocks to Intraoperative Nerve Block Catheters for Breast Reconstruction: A Prospective Randomized Trial

Protocol Version Date: 6/21/18

2) Objectives

Aim 1: Report the efficacy and safety of pectoralis nerve blocks for breast reconstruction surgery in a prospective fashion

- Hypothesis: we anticipate >90% efficacy of all pectoralis nerve blocks and no complications

Aim 2: Comparison of intraoperative versus preoperative placement of pectoralis nerve blocks

2A: Comparison of block efficacy and safety

- Hypothesis: We anticipate a significantly better block efficacy with intra-operatively placed block catheters as opposed to pre-operatively placed blocks, as intra-operatively placed blocks are done under direct visualization and can be left in place. We anticipate no difference in safety profile.

2B: comparison of secondary outcomes, such as cost, block placement time, post-op nausea/vomiting, patient satisfaction, and operative times.

- Hypothesis: We anticipate a faster overall time (From admission to clearance for PACU discharge) with intra-operatively placed blocks. We anticipate use of less inhalational anesthesia with pre-operatively placed blocks. We anticipate no difference in secondary outcomes, such as post-operative nausea and vomiting, narcotic use and patient satisfaction between the two block groups.

3) Background

Level 1 data shows improved post-operative analgesia with decreased anesthetic and opiate use, decreased hospital length of stay, and improved patient satisfaction scores with the use of regional nerve blockade.¹⁻⁵ Using nerve blocks to limit general anesthesia (GA) and improve post-operative analgesia is additionally important due to the mounting evidence that volatile anesthetics and opioid analgesics impair immune function^{6,7}, and increase the risk of ileus, thromboembolism and myocardial infarction⁸. Despite these advantages, the use of regional nerve blockade is still limited to selected cases.

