Information will be collected from all subject's hospital stays, including time in pre-op holding area, time under general anesthesia, duration inhalational anesthetic, amount of narcotic used in morphine equivalents (divided into OR amount, and amounts in first 6, 12, 18 and 24 hours after surgery) after surgery, incidence of nausea/vomiting, number and amount of antiemetic used (same time intervals as above), pain scores overall and by breast on the 0-10 analog scale (average over the same time intervals), time of PACU clearance, and time of hospital discharge. In addition, a RedCaps survey with questions about the patient's pain level will be emailed pre-op and at post-op hours 6,12,24 and days 2-7.

For patients with pain catheters, these catheters will be removed at the patient's regularly scheduled post-operative appointment (generally POD 4 or 5). On-Q balls will not be refilled such that all catheter patients will have infusion for the same amount of time.

One week after hospital discharge, subjects will be emailed a short survey through the RedCap survey system (see supplemental forms for survey questions). Hospital billing

PROTOCOL TITLE:

will be examined with the assistance of the billing department using CPT codes and using publically available cost data.

8) Data and/or Specimen Management and Confidentiality

During the review, the investigator (or research staff) will record data collected in a manner that includes indirect identifiers. Additionally, a single location will include indirect and direct identifiers (to match the two).

To elaborate: Subjects will be identified by a unique study ID (A = pre-op placement, B = intra-op placement; so 1A would be the first patient enrolled in the pre-op placement group). An enrollment log, including a “crib sheet” identifying patients by their study ID and their consent paperwork, will be kept in a binder. That binder will be stored in a locked cabinet in the plastic surgery Lab in Research Building 2. After the IRB has been closed, study consents will be maintained for 3 years, and HIPAA consents for six years, in compliance with IRB rules and regulations. Any data compiled off of the Electronic Medical Record (EMR) will be identified by subject ID only and collected onto a spreadsheet on the PI’s password protected computer.

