With respect to the surveys, Redcap is a mature, secure web application that has been used successfully by many other investigators at our institution to collect secure survey data.

Data analysis will be done using <http://vassarstats.net>. Statistical comparisons will be performed across the study groups using T-test for two-group comparisons.

All research personnel will be up to date with their HIPAA training.

For our power analysis, we set our alpha = 0.05 and beta (power) = 0.8. Using the Bashandy et al. paper¹, the mean morphine requirement in the PACU was 2.9 ± 1.861 mg for the Pecs block group, and 6.9 ± 1.861 mg for the control group ($p < 0.001$). Based on our preliminary experience with pre-operatively placed pecs blocks, we estimate that they work well about 70% of the time. If we hope to see a 20% improvement with more accurate plane targeting, then our average morphine requirement in the intra-operative placement group would be 2.3 mg. Therefore, we would have to enroll 126 patients in each arm to have an 80% chance of seeing a difference, if there truly is one.

9) Provisions to Monitor the Data to Ensure the Safety of Subjects

The EMR of every subject who completes the injection portion of this study will be assessed within 24 hours of pectoralis nerve block placement. Any untoward events, such as intravascular injection, allergic reaction, pneumothorax or other unanticipated event will be assessed for its causative relationship to the pectoral nerve block . We anticipate these to all be very unlikely, as the current literature on the pectoralis nerve blocks report a 0% complication rate (see citations, above). If a serious adverse event occurs, these will be reported immediately to the IRB and will be a trigger for an immediate suspension in enrollment and a review of the injection protocol with the Chiefs of both the Departments of Anesthesiology and Surgery. If any performer error can be identified and corrected, then with approval from the departments enrollment will continue. If not, the study will be terminated.

We will cumulatively review the data after 20 subjects in each study arm have been enrolled, and then again at 50 patients, 75 patients, 100 patients, and 126 patients.

10) Withdrawal of Subjects

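### The one statistical method named, a two-group t-test, gives no result at the zero complications predicted and no estimate or limit for Aim 1's pooled rate, so the safety claims would carry no statement of uncertainty.

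*Combined protocol and SAP*

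**What the plan says.** Safety is an objective twice in Section 2. Aim 1 is to "Report the efficacy and safety of pectoralis nerve blocks for breast reconstruction surgery in a prospective fashion", with the hypothesis "we anticipate >90% efficacy of all pectoralis nerve blocks and no complications". Aim 2A compares the two arms and adds "We anticipate no difference in safety profile".

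The analysis is described in Section 8: "Data analysis will be done using <http://vassarstats.net>", followed by "Statistical comparisons will be performed across the study groups using T-test for two-group comparisons". No other test, no confidence interval and no one-sample method is named anywhere. The power calculation in the same section concerns PACU morphine only.

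Section 6 sets 126 patients per arm, 252 in all, and says that no particular safety endpoints are defined. Section 7 lists another yes/no outcome, "incidence of nausea/vomiting". Section 9 provides for a chart check within 24 hours of block placement, case-by-case causality assessment and suspension of enrolment after a serious event. It justifies the expectation of few events by saying that "the current literature on the pectoralis nerve blocks report a 0% complication rate".

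**The concern.** A complication either happens to a patient or does not, and the protocol expects it to happen to nobody. The only planned method compares two means. It breaks down if the expected result occurs, because neither arm then has any variation. It also does not address Aim 1, which concerns one rate over all blocks and not a contrast between arms.

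What is at stake is the strength of the safety conclusion. Zero events in a trial of this size is compatible with a range of true rates. Section 11 itself says that the rare events could have serious consequences. If the plan is followed as written, a finding of no complications and no safety difference would be stated without that range, and would read as stronger than the data allow.

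**Working it through.** **Inputs.** 126 patients per arm and 252 in total (Section 6); predicted complications 0 (Section 2, Aim 1); method, two-group t-test (Section 8). The documents give no figure for precision on complications, so there is no stated safety figure to reproduce. The 126 comes from the morphine calculation and is taken here as given.

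**1. The t-test at the predicted result.** With 0/126 in each arm the mean difference is 0 and both sample variances are 0, so t = 0/√(0 + 0), which is undefined. Run on two vectors of 126 zeros, the pooled and the Welch versions both return no value. With 1/126 against 0/126 the pooled test does run (t = 1.00, p = 0.318), so the failure is specific to zero events in both arms.

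**2. How likely that result is.** The true rate is not in the documents, so a range is shown. P(no events in 252) = (1 − p)^252.

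| Assumed true rate | P(0 of 252) |
|---|---|
| 0.2% | 0.604 |
| 0.5% | 0.283 |
| 1.0% | 0.079 |

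**3. What zero events would support.** With 0 events in n patients, the exact (Clopper-Pearson) two-sided 95% upper limit is 1 − 0.025^(1/n); the one-sided limit uses 0.05.

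- Pooled: 1 − 0.025^(1/252) = 1.45% (one-sided 1.18%).
- Per arm: 1 − 0.025^(1/126) = 2.89% (one-sided 2.35%).

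**4. Difference between arms.** The Wilson upper limit for 0/126 is z²/(n + z²) = 3.841/(126 + 3.841) = 0.0296. The Newcombe 95% interval for 0/126 minus 0/126 is therefore −2.96 to +2.96 percentage points.

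**5. Sensitivity to the denominator.** Section 10 stops data collection when expander placement is aborted, although patients in the pre-operative arm have by then received the block. The number lost is not given. If 240 patients had safety data, the pooled limit would be 1 − 0.025^(1/240) = 1.53%; with 230 it would be 1.59%.

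**6. Nausea and vomiting, for contrast.** With illustrative counts of 38 and 25 of 126, the t-test gives p = 0.0590 and the chi-square test p = 0.0586. For an outcome this common, the choice of test hardly affects the p-value.

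**The case against.** The best case for the plan has several parts.

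- *Aim 1 only promises to report.* The t-test sentence covers comparisons across groups, so a simple count for Aim 1 is implied and an interval is not excluded. This stands as far as it goes: the absence of a bound is inferred from the plan's silence. But Aim 1 carries a hypothesis, and a bare count does not show how far the data support it.
- *An undefined statistic misleads nobody.* With no events in either arm no test is informative; Fisher's exact test gives p = 1. This also stands. The harm is the missing interval, and 0/0 is only its symptom.
- *Safety is monitored.* Section 9 does protect participants through case review and suspension of enrolment. It does not estimate a rate.
- *An exact limit may look firmer than the data.* This stands and shapes the fix. The chart check is within 24 hours of placement, whereas catheters stay in until about day 4 or 5 (Section 7), and the added catheter risk named in Section 11 is post-operative infection.

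Two stronger readings are tempting. A reader might infer that the t-test would produce false safety signals when events are few. The design does not support that: with 126 per arm and equal true rates between 0.2% and 5%, the t-test's false-positive rate stays at or below 5%. A reader might also infer that the report would contain no usable number. It would give 0 of 252, from which anyone can derive the limit. The defect is that the plan does not commit to stating it.

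**Conclusion.** The point holds as an omission that should be put right. The plan specifies no estimate, interval or workable test for complications, although two aims make claims about them. If the prediction comes true, the data would support a complication rate below about 1.5% overall and below about 2.9% in each arm, with a difference between arms within about ±3 points. They would not establish that complications do not occur or that the arms are equally safe.

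These figures assume that all 252 patients received a block and have safety data, that the patient is the unit of analysis (Section 7 records pain by breast, so blocks and patients may differ in number), and that only events found in the stated chart-review window are counted. With fewer patients the limits widen, and for later events they say nothing. The documents name no complication rate that would be unacceptable, so it cannot be said whether 1.5% is reassuring. The morphine comparison is unaffected, and for nausea and vomiting the gain is in presentation only.

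**What to change.** In Section 8:

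- Limit the t-test to continuous outcomes.
- Report the complication rate overall and by arm with exact (Clopper-Pearson) 95% intervals.
- Compare arms by the risk difference with a Newcombe 95% interval and Fisher's exact test, named in advance.
- Report nausea and vomiting as a risk difference with a 95% interval.

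In Aims 1 and 2A, state that zero events in 252 patients would support a rate below about 1.5% (below about 2.9% per arm, and a difference within about ±3 points). Define the denominator as patients who received a block and have safety data, and say that the statement covers only events captured in the chart-review window of Section 9. Recalculate the limits from the number actually observed.

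The cost is a few sentences, with no new data and no more patients. The downside is a slightly less favourable safety claim.

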department is already performs pectoralis nerve blocks on selected patients, and have the work flow set up for this. The dose will be 10 mL of 0.25% Ropivacaine for the pecs 1 injection, and 20 mL of 0.25% Ropivacaine for the pecs 2 injection. Ropivacaine is a standard sodium channel blocking anesthetic already FDA approved for peripheral nerve blocks. For those randomized to the intra-operative arm, catheter placement will be performed after the pectoralis muscle flap has been raised, for more accurate targeting of the tissue planes and nerves. Blocks will be performed by the operating surgeon. Instead of single shot blocks, a commercially available On-Q nerve block catheter (Halyard Health, Alpharetta, Georgia) will be placed. Through these catheters, 0.2% Ropivacaine will be instilled at 4 mL/hr for a total of 400 mL (amount in standard On-Q reservoirs). Vitals are continuously monitored in the operative suite and in the Post Anesthesia Care Unit (PACU), with a high level of supervision by the anesthesiology team. In the very rare event of an adverse reaction to the injection, appropriate action will be taken immediately and in accordance with standard work-flow for local anesthetic toxicity (epinephrine for severe allergy or circulatory support, intravascular lipid emulsion and sodium bicarbonate for overdose, although our doses should not be high enough to precipitate this, even with inadvertent intravascular injection). If hypoxia not due to opioids and not responsive to supplemental oxygen is present, a chest radiograph will be ordered to rule out pneumothorax from inadvertent visceral pleural puncture.

Post-operatively, the patients will be monitored in the PACU. They will have standard anesthesia pain and nausea management orders written for (these are ordered en bloc as part of an already existing order set). PACU nursing staff will dose medications according to the written orders. PACU clearance time (which is currently time-stamped in the chart by the PACU resident) will be noted. Often patients will remain in PACU due to ward over-crowding, so actual time of PACU discharge will not be noted. Post-PACU hospital course will proceed as is standard of care, with PRN pain and nausea medication ordered. Standard hospital discharge criteria will be used for all groups.

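### The sample size and its 80% power rest on PACU morphine, which the plan neither lists as an opioid amount to be collected nor names as an outcome

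*Combined protocol and SAP*

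**What the plan says.** All references are to the combined protocol and SAP.

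- **Section 8, power analysis.** "we set our alpha = 0.05 and beta (power) = 0.8". The reference figure is from a cited Pecs block trial: "the mean morphine requirement in the PACU was 2.9 ± 1.861 mg for the Pecs block group". A 20% improvement, credited to reaching the tissue planes more accurately, leads to the assumption that "our average morphine requirement in the intra-operative placement group would be 2.3 mg". The result is 126 patients per arm. The analysis is one sentence: "Statistical comparisons will be performed across the study groups using T-test for two-group comparisons". Sidedness is not stated.
- **Section 7, data collected.** Narcotic use in morphine equivalents is "divided into OR amount, and amounts in first 6, 12, 18 and 24 hours after surgery". PACU clearance time is recorded; the time of actually leaving the PACU is not.
- **Section 6, endpoints.** The primary endpoint is described as completion of the study by 252 patients. Time to PACU clearance and time to hospital discharge are secondary.
- **Section 2, objectives.** Aim 2A expects better block efficacy with catheters because "intra-operatively placed blocks are done under direct visualization and can be left in place". Block efficacy is not defined. Aim 2B lists narcotic use among the secondary outcomes on which the arms are expected not to differ.
- **Section 7, regimens.** The pre-operative arm receives 10 mL of 0.25% ropivacaine for the first injection and "20 mL of 0.25% Ropivacaine for the pecs 2 injection", before surgery. In the catheter arm, "0.2% Ropivacaine will be instilled at 4 mL/hr for a total of 400 mL". The catheter replaces the single-shot block, and no bolus through it is described.

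**The concern.** A power statement is useful only if it refers to the variable on which the trial will be judged. Here the only opioid variable with a mean and SD is PACU morphine, and it is absent from the list of opioid amounts and from the endpoints. The first-6-hour total may contain most of the PACU stay, but it is a different variable, and the plan gives no SD for it. A reader of the final report could not tell which opioid comparison the 252 patients were meant to support, and the choice could be made after the data are seen.

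Timing adds a caveat. One arm receives its whole dose before surgery and the other receives a slow infusion that starts during surgery. Part of the rationale for the catheter is that it stays in place. An early window may therefore understate a benefit that builds up later, and a null result in the PACU could not be read as absence of that benefit.

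**Working it through.** **1. The plan's own sample size.** Inputs from section 8: means 2.9 and 2.3 mg, SD 1.861 mg, alpha 0.05, power 0.80. Allocation is 1:1 (section 6). The difference is 2.9 − 2.3 = 0.6 mg, or 0.20 × 2.9 = 0.58 mg before rounding.

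n per arm = 2 × (z_alpha + z_power)² × SD² / difference², with SD² = 3.463.

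| Test | Difference | Calculation | n per arm |
|---|---|---|---|
| Two-sided | 0.60 | 2 × (1.960 + 0.842)² × 3.463 / 0.360 | 152 |
| Two-sided | 0.58 | 2 × (1.960 + 0.842)² × 3.463 / 0.336 | 162 |
| One-sided | 0.60 | 2 × (1.645 + 0.842)² × 3.463 / 0.360 | 119 |
| One-sided | 0.58 | 2 × (1.645 + 0.842)² × 3.463 / 0.336 | 128 |

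The stated 126 is close to the one-sided result with the unrounded effect (128). It also equals 119 / 0.95 rounded up, but the plan states no 5% dropout allowance. No two-sided variant gives 126.

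**2. Power at 126 per arm if PACU morphine is kept.** Two-sided, 0.6 mg: the standard error is 1.861 × √(2/126) = 0.2345, 0.6 / 0.2345 = 2.559, and 2.559 − 1.960 = 0.599, so power is 73%. For 0.58 mg it is 70%. One-sided, the figures are 82% and 80%. If the true PACU difference were smaller (assumed values), two-sided power would be 48% at 0.45 mg and 25% at 0.3 mg.

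**3. Sized variable against the rest of the plan.**

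| Place | Opioid variable |
|---|---|
| Section 8, sizing | PACU morphine |
| Section 7, listed amounts | OR; first 6, 12, 18 and 24 hours |
| Section 6, primary endpoint | None (completion of 252 patients) |
| Section 2, Aim 2B | Narcotic use, secondary, no difference expected |

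The first row appears in none of the others.

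**4. Timing of the two regimens (section 7).** Pre-operative arm: (10 + 20) mL × 2.5 mg/mL = 75 mg at once. Catheter arm: 4 mL/h × 2 mg/mL = 8 mg/h for 400 / 4 = 100 hours.

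| Hours of infusion | One catheter, mg | Share of 75 mg |
|---|---|---|
| 1 | 8 | 11% |
| 2 | 16 | 21% |
| 4 | 32 | 43% |
| 6 | 48 | 64% |
| 12 | 96 | 128% |
| 24 | 192 | 256% |

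One catheter reaches 75 mg after 75 / 8 = 9.4 hours. Two catheters at 4 mL/h each against a single 75 mg block, which is an assumption, reach it after 75 / 16 = 4.7 hours. If both regimens apply per side, the shares in the table do not change. PACU length and the time from the start of infusion to the PACU are not stated, so no row can be identified as the PACU.

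**5. What 126 per arm can detect in a later window.** The plan gives no mean or SD for any listed window, so a corrected sample size cannot be computed. Detectable difference (two-sided 0.05, 80% power) = SD × (1.960 + 0.842) × √(2/126) = 0.353 × SD. For assumed SDs of 3, 4, 5 and 6 mg this is 1.06, 1.41, 1.76 and 2.12 mg.

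**The case against.** Four points can be made for the plan.

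- **The early window suits the effect that was sized.** Section 8 credits the 20% to accurate placement, which could act as soon as the infusion starts. A reader might infer from the dose arithmetic that the catheter's advantage has not begun in the PACU, or that the comparison would reverse there. The documents do not support this. Aim 2A gives two reasons for the catheter, and milligrams delivered are not analgesic effect. This stands, so the timing is only a caveat.
- **PACU morphine may be recoverable.** The section 7 list is not worded as exhaustive, the data come from the medical record, and clearance time is recorded. Opioid use up to clearance could perhaps be derived. It would therefore be too strong to say that the variable cannot be obtained. But the plan does not commit to deriving it.
- **Later benefit is already measured**, through opioid use to 24 hours and pain surveys on days 2 to 7. That is correct, but none of these is named as primary or has a power figure.
- **A 24-hour opioid outcome has its own problems.** Aim 2B expects no difference in narcotic use, section 7 draws opioid data from the hospital stay, and 24 hours is about a quarter of the 100-hour infusion. These points stand and are taken up in the fix.

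A reader might also infer that greater opioid use in the operating room in the catheter arm would lower its PACU requirement. The documents give no figure for this, and the OR amount is collected separately. It remains conjecture.

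**Conclusion.** The concern holds as a mismatch between the sized variable and the plan's outcomes. The 126 per arm and 80% power refer to PACU morphine, which is not a listed opioid amount and is not named as an outcome anywhere, so the power applies to no listed outcome. This follows from the text and needs no assumption.

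Two sizes can be given. For PACU morphine itself, two-sided power at 126 per arm is about 73% for 0.6 mg (70% for 0.58 mg); the shortfall from 80% depends on the test being two-sided, which the plan leaves open. For a listed window, 126 per arm detects 0.353 SD, and the value in milligrams depends on an SD that the plan does not supply.

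The timing argument supports only this: an early window may understate a benefit that comes from the catheter staying in place. A missed or reversed effect is not demonstrated, because PACU length, infusion start and number of catheters are unstated. The plan should be changed, since the repair is mainly one of wording.

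**What to change.** Leave both regimens as they are, and:

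1. Name one opioid window that is already collected as the primary outcome for Aim 2A. Cumulative morphine equivalents over 0-24 hours is the natural choice, because Aim 2A also relies on the catheter remaining in place.
2. State how patients discharged before 24 hours are handled.
3. Report the OR amount and the 0-6 hour amount beside it.
4. Reconcile this with Aim 2B, which lists narcotic use as secondary with no difference expected, and replace the section 6 primary endpoint with the named outcome.
5. Restate the power for that outcome with an explicit mean, SD and two-sided test, showing a range of SDs if no source is available.

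Alternatively, keep PACU morphine: name it as primary, add opioid use up to the recorded PACU clearance time to the data list, and correct the power to about 73% for 0.6 mg two-sided, or raise the sample size to 152 per arm (162 for 0.58 mg).

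The cost is wording and a recalculation. The 0-24 hour option needs no new in-hospital data, but if some patients leave before 24 hours, the rule for them may require opioid use after discharge to be recorded. The cited PACU SD no longer applies under that option, so a new SD assumption is needed and the restated power may be less favourable.

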
6) Study Endpoints

The primary study endpoint will be after completion of study (after surgery and survey completion) of 252 patients (126 in each treatment arm). Secondary endpoints include time to PACU clearance and time to hospital discharge. Because the intervention is a single-shot injection, there are no specific safety endpoints. Please see below for a discussion of potential adverse from the pectoralis nerve blocks.

7) Procedures Involved

Subjects presenting for immediate breast reconstruction and meeting inclusion criteria will be approached pre-operatively to make them aware of the study. On the day of surgery, patients will be asked to sign consent for the study. Patients who sign consent will then undergo randomization to a study arm (pre-op placement of intra-op catheter placement). Randomization will be done by study personnel using the i-phone application “Randomizer.” Randomization will follow a blocked scheme; that is, if one patient is randomized to the anesthesia block group, the next will automatically get the catheter treatment. This will ensure equal numbers in both study arms. After consent and randomization is complete, patients will be told of their study arm. Patients will then be asked to fill out a pre-operative pain survey discussing their baseline level of breast pain.

For those randomized to the pre-op placement arm, anesthesia will perform this block prior to surgery but after their pre-operative survey is complete. The anesthesia

PROTOCOL TITLE:

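### The t-test's sidedness is not stated: for 2.9 vs 2.3 mg, 126 per arm gives about 82% power one-sided but only about 72% two-sided, against a claimed 80%

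*Combined protocol and SAP*

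**What the plan says.** The sample size paragraph is in section 8 (Data and/or Specimen Management and Confidentiality). It opens with "we set our alpha = 0.05 and beta (power) = 0.8". It takes its inputs from a cited randomized trial of pecs blocks, where "the mean morphine requirement in the PACU was 2.9 ± 1.861 mg for the Pecs block group". It then supposes a 20% improvement with intra-operative placement, so that "our average morphine requirement in the intra-operative placement group would be 2.3 mg". From this it concludes that "we would have to enroll 126 patients in each arm to have an 80% chance of seeing a difference, if there truly is one". Section 6 repeats the total of 252 patients.

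The only description of the analysis, also in section 8, is "Statistical comparisons will be performed across the study groups using T-test for two-group comparisons". No section says one-sided or two-sided.

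The hypotheses in section 2 do not settle it. Aim 2A is directional: "We anticipate a significantly better block efficacy with intra-operatively placed block catheters as opposed to pre-operatively placed blocks". Aim 2B, however, lists narcotic use among the outcomes on which the two arms are expected not to differ.

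**The concern.** For fixed means, SD and sample size, moving from a one-sided to a two-sided test at 0.05 costs about ten percentage points of power here. A reader would normally assume two-sided, and on that reading 126 per arm does not deliver the stated 80%.

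Two things are at stake. First, this calculation is the only reason given for enrolling 252 patients, so if it is off, the trial's chance of detecting its target effect is overstated. Second, the choice of test can change the conclusion. There is a band of observed differences that is significant one-sided and not significant two-sided. Section 9 plans cumulative data reviews at 20, 50, 75, 100 and 126 patients, so the choice should be fixed before results are seen.

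**Working it through.** **Inputs, all from section 8.** Alpha 0.05; target power 0.80; mean 2.9 mg in the pre-operative arm; mean 2.3 mg in the intra-operative arm; SD 1.861 mg (taken as equal in both arms); 126 per arm; two-sample t-test.

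**Size of the assumed difference, d.** The text allows three readings:
- printed mean: 2.9 − 2.3 = 0.60 mg
- exact 20% cut: 0.20 × 2.9 = 0.58 mg, mean 2.32 mg
- success rising from 70% to 90%, with morphine scaled in proportion: 2.9 × 70/90 = 2.26 mg, d = 0.644 mg

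**Step 1: reproduce 126.** Normal approximation, n per arm = 2(z_α + z_β)² SD² / d²:
- one-sided, d = 0.58: 2(1.645 + 0.842)² × 1.861² / 0.58² ≈ 127.3, so 128
- one-sided, d = 0.60: ≈ 119.0, so 119
- two-sided, d = 0.60: 2(1.960 + 0.842)² × 1.861² / 0.60² ≈ 151.0, so 152
- two-sided, d = 0.58: ≈ 161.6, so 162

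The stated 126 is approximated only one-sided, most closely with the exact 20% cut. Inflating 119 for 5% dropout also gives 126 (119/0.95 = 125.3), but the plan states no dropout allowance, and that route is one-sided too.

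**Step 2: power at 126 per arm.** The standard error of the difference is 1.861 × √(2/126) = 0.2345 mg. For d = 0.60 the standardized difference is 0.60/0.2345 = 2.559. Normal approximation:
- two-sided: Φ(2.559 − 1.960) = Φ(0.599) = 72.5%
- one-sided: Φ(2.559 − 1.645) = Φ(0.914) = 82.0%

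The noncentral t with 250 degrees of freedom gives:

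| Assumed mean (mg) | d (mg) | Two-sided power at 126 | n per arm for 80%, two-sided | One-sided power at 126 | n per arm for 80%, one-sided |
|---|---|---|---|---|---|
| 2.25 | 0.65 | 78.9% | 130 | 86.9% | 103 |
| 2.26 | 0.644 | 78.2% | 132 | 86.3% | 104 |
| 2.30 | 0.60 | 72.2% | 152 | 81.8% | 120 |
| 2.32 | 0.58 | 69.3% | 163 | 79.5% | 128 |
| 2.35 | 0.55 | 64.7% | 181 | 75.6% | 143 |

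The rows 2.25 and 2.35 bound every mean that would print as 2.3 mg. Two-sided power does not reach 80% anywhere in that range.

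**Step 3: detectable difference.** With 126 per arm and 80% power, it is 0.659 mg two-sided (0.659/2.9 = 23% of the pre-operative mean) and 0.585 mg one-sided (20%).

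**Step 4: where the choice changes the result.** The smallest significant observed difference is t × 0.2345, which is 0.462 mg two-sided and 0.387 mg one-sided. An observed reduction between about 0.39 and 0.46 mg is significant under one test and not under the other.

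**Step 5: a different basis for 126.** Treating block success as a proportion does not rescue a two-sided reading. For 70% vs 90%, the two-sided requirement is 62 per arm, or 72 with continuity correction. For 70% vs 84% it is 141, or 155. One variant lands near 126 (70% vs 84%, one-sided, continuity-corrected: 125), but it is also one-sided, and the text derives its number from mean morphine.

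**The case against.** The omission and the arithmetic are hard to dispute. The case on the other side concerns how large the shortfall is and what follows from it.

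- **The 72% belongs to one reading.** The plan says blocks work about 70% of the time and then speaks of a 20% improvement, without saying whether that is relative or in percentage points. Read as 70% to 90%, the mean is 2.26 mg and two-sided power is 78.2%, a gap of about 2 points rather than 8. This stands as a caution about size, but even that reading falls short of 80%.
- **A one-sided test is not shown to have been used.** It calls for 120 or 128 per arm, not exactly 126. That is right: the figures show compatibility, not what the sponsor did.
- **Direction.** Aim 2A might suggest a one-sided test, but the trial is sized on morphine, and Aim 2B expects no difference in narcotic use. The power sentence also speaks of a difference without direction. This weakens any implied one-sided test and so makes the two-sided shortfall more relevant.
- **The decisive band is narrow.** It is about 0.075 mg wide. For reductions outside it the two tests agree. That is true, but it is no reason to leave the test open.
- **Keeping 126 gives up the 80% target.** The sponsor could instead enlarge the trial to about 152 per arm (132 to 163 across the three readings). That option is open, but correcting the statement does not require it.

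**Conclusion.** The concern holds. The plan does not state sidedness, and under a conventional two-sided t-test at 0.05 the claimed 80% power at 126 per arm is not attained. Power is 72.2% for the printed means, 69.3% for an exact 20% reduction, and at most 78.9% for any mean that rounds to 2.3 mg. The stated figure is approximately reached only with an undeclared one-sided test.

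This rests on the SD of 1.861 mg as printed, equal in both arms, with all 126 patients per arm analysed. The source of that SD was not checked. It should be corrected but is not fatal: the design can stand with an accurate power statement.

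**What to change.** In section 8:

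1. Add that the t-test is two-sided at 0.05.
2. Give the unrounded mean assumed for the intra-operative arm, and say whether the 20% is relative or in percentage points.
3. Keep 126 per arm and restate the power, for example: *With 126 per arm, SD 1.861 mg and a two-sided t-test at 0.05, power is about 72% for 2.9 vs 2.3 mg; the difference detectable with 80% power is 0.66 mg.* If the unrounded mean is 2.32 or 2.26 mg, the power figure becomes about 69% or 78%; the 0.66 mg is unchanged.
4. If a one-sided test was intended, say so, justify it, and commit the final analysis to the same one-sided test.

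The cost is one corrected paragraph and one added word in the analysis sentence. No extra patients are required; the only downside is a less favourable stated power.
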